 - Participants' characteristics ascertained at baseline will be compared across intervention groups using independent samples or Wilcoxon rank sum tests, as appropriate, for continuous variables and a chi-square or Fisher's exact tests, as appropriate, for categorical variables. Although no significant differences are expected due to the randomized intervention assignment and the relatively large sample size, any variables found to be significantly different will be noted and accounted for, by controlling for them as covariates in supplements to the main analyses.
- *Time-specific and change scores*. Scores at each follow-up and change in mean scores from baseline at 24 weeks, by intervention group, for all outcome measures will be calculated and presented.
- *Intervention adherence, attrition, and retention*. Class attendance data will be calculated as the average number of scheduled intervention sessions (48 total) attended by participants across intervention groups. Study attrition and retention rates will also be calculated and reported, by intervention group, as the number of participants who completed the 24-week intervention and those who completed all scheduled study follow-up assessments.

Analysis populations

Efficacy analyses. The effect of intervention on the co-primary study outcomes will be evaluated using an intention-to-treat approach in which participants will be analyzed according to randomization assignment. A modified intention-to-treat analysis will be conducted that includes all participants who have undergone randomization and have completed all study follow-up assessments, regardless of their participation adherence status. Finally, a per-protocol analysis will include participants in the intention-to-treat population who have an overall class attendance rate of $\geq 75\%$ (out of the total planned 48 intervention class sessions) of their assigned exercise intervention.¹⁰

Co-primary endpoint analyses

To test the *Primary hypothesis*, we plan to use a generalized linear mixed model with random intercepts and fixed treatment effects for the primary outcomes. Specifically, we will determine the intervention effect through an analysis of a 3 (Group) by 3 (Time) mixed-effects model with repeated measures (follow-up time point) on the second factor (i.e., outcome measures assessed at baseline, 4 months [mid-point], and 6 months [intervention termination]).

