In the presence of a Group by Time interaction effect, follow-up pair-wise comparisons, using independent t tests, will be performed to identify a priori specified between-group differences. Specifically, we will determine the intervention effect of cognitively enhanced tai ji quan for change in MoCA and costs of dual task in gait performance from baseline to 24 weeks by making a comparison between cognitively enhanced tai ji quan and standard tai ji quan and between cognitively enhanced tai ji quan and stretching exercise.

Level of statistical significance and confidence intervals. Our primary outcome analyses will be 2-sided with an adjusted significance level of <0.0125 (0.05 / 4 comparisons) and a 98.75% confidence interval (CI). For each group, both estimated means and their corresponding standard error of estimates at each assessment point will be presented. In presenting between-group differences, mean differences with CIs will be presented. SPSS "MIXED" function will be used in analyzing our primary outcomes.

Secondary and tertiary outcome analyses

A similar analytic approach will also be applied to all secondary and tertiary (continuous) outcome variables described in Table 1. All study outcomes are expected to follow a normal distribution. In the case of deviation from normality, generalized estimating equations will be used to assess the effect of intervention over time. No Bonferroni correction will be made to account for multiple comparisons.

Level of statistical significance and confidence intervals. All tests and CIs will be 2-sided, and statistical significance will be defined as a P value of <0.05. For each group, we will report both estimated means and their corresponding standard error of estimates at each assessment point. In presenting between-group differences at 24 weeks, estimated mean differences with CIs will be presented.

Analyses on examining intervention durability at 48-week follow-up

We will use the same analytic strategy outlined in our primary and secondary outcome analyses, with the exception of CDR-SB (described in detail below), to examine whether the intervention effects will persist 24 weeks after the end of the 24-week supervised interventions (*Secondary hypothesis*).

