Note: Group is a binary variable involving a comparison between cognitively enhanced tai ji quan and standard tai ji quan or cognitively enhanced tai ji quan and stretching exercise.

Post-hoc exploratory analyses

No pre-specified post-hoc exploratory analyses are planned.

Subgroup analyses

In light of the findings reported in prior studies, 36,37 we also plan to conduct a series of subgroup analyses. Specifically, using a three-way interaction model that involves factors of Group, Time, and Subgroup, we will examine whether the expected between-group differences in the two primary outcomes are associated with pre-specified subgroups that include sex (1 = men, 2 = women), age (1 = 65-74, 2 = 75-84, 3 = 85+ years old), and level of education (1 = high school diploma or lower, 2 = college degree or higher). We are aware of the fact that these subgroup analyses are not powered statistically, and we will therefore interpret any statistically significant results with caution. All subgroup analyses are based on an alpha level of <0.05.

Power estimation for primary outcomes

This study is powered to detect a mean difference in change in the primary outcomes of MoCA and motor-cognitive dual-task gait performance between (a) the cognitively enhanced tai ji quan intervention and a standard tai ji quan intervention operationalized by TJQMBB, ¹⁰ and (b) the cognitively enhanced tai ji quan intervention and a non-tai ji quan control condition – stretching – at 6 months, among older adults with MCI. We estimated the magnitude of the effect size (difference score divided by its pooled standard deviation) that is detectable with at least 80% power using a 2-sided 0.05-level test. We expect that participants in the cognitively enhanced tai ji quan intervention would experience a clinically meaningful improvement of at least 1 score unit in MoCA and a 10% reduction in dual-task costs on gait performance speed between the enhanced tai ji quan intervention and each of the two comparison arms. The following details the parameters used and results of our power analyses for each of the two primary outcomes.

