 $\underline{\text{MoCA}}$. Assuming two (pre and post) repeated measurements and a between-level correlation of 0.7, the planned sample size of 267 participants would provide >80% power to detect a medium-size difference (Cohen d = 0.4) in mean MoCA change of 1.5 points (SD = 3.5) between the cognitively enhanced tai ji quan and the standard tai ji quan groups and a large-size difference (Cohen d = 0.8) of 3 points (SD = 3.5) between the cognitively enhanced tai ji quan and the stretching control groups at 6 months. No minimal clinically important difference (MCID) in MoCA has been established in the physical exercise literature, but our target estimate is close to that of 1.22 points established for the stroke patient population.³⁸

Dual-task gait performance. Using the same assumptions, at 6 months, we estimated a 10% reduction in dual-task walking costs between the cognitively enhanced tai ji quan and standard tai ji quan interventions and a 20% reduction between cognitively enhanced tai ji quan and stretching interventions. At the time of developing this research proposal, no MCID for reduction in costs in dual-task performance in gait is available. The target estimates calculated in this trial were inferred from our prior completed studies. ^{10,12}

Taking into account a conservative 15% loss during the 6-month active intervention period, a total of 315 participants was planned for the study.

Treatment of noncompliance and missing data

All enrolled study participants will be followed until the trial period ends, whether or not the participant is still receiving or complying with the intervention. Primary endpoint analyses will be conducted according to the original randomization scheme in an intention-to-treat approach. We will use a multiple imputation data method for missing data. We plan to perform 10 sets of imputations. Variables without missing data to be used for prediction of imputed values on the study variables will include baseline measures of age, sex, level of education, MMSE, number of chronic conditions, and depression. The imputed data will be submitted to the same analytic model (i.e., linear mixed model) as the non-imputed observed data, and the results of each analytic model will be pooled across the 10 imputed data

sets. The secondary outcome analyses will also be conducted using the multiple imputation method described above. Tertiary outcome analysis will be conducted with observed data without imputation.

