Efficacy analyses. The effect of intervention on the co-primary study outcomes will be evaluated using an intention-to-treat approach in which participants will be analyzed according to randomization assignment. A modified intention-to-treat analysis will be conducted that includes all participants who have undergone randomization and have completed all study follow-up assessments, regardless of their participation adherence status. Finally, a per-protocol analysis will include participants in the intention-to-treat population who have an overall class attendance rate of $\geq 75\%$ (out of the total planned 48 intervention class sessions) of their assigned exercise intervention.¹⁰

Co-primary endpoint analyses

To test the *Primary hypothesis*, we plan to use a generalized linear mixed model with random intercepts and fixed treatment effects for the primary outcomes. Specifically, we will determine the intervention effect through an analysis of a 3 (Group) by 3 (Time) mixed-effects model with repeated measures (follow-up time point) on the second factor (i.e., outcome measures assessed at baseline, 4 months [mid-point], and 6 months [intervention termination]).

In the presence of a Group by Time interaction effect, follow-up pair-wise comparisons, using independent t tests, will be performed to identify a priori specified between-group differences. Specifically, we will determine the intervention effect of cognitively enhanced tai ji quan for change in MoCA and costs of dual task in gait performance from baseline to 24 weeks by making a comparison between cognitively enhanced tai ji quan and standard tai ji quan and between cognitively enhanced tai ji quan and stretching exercise.

Level of statistical significance and confidence intervals. Our primary outcome analyses will be 2-sided with an adjusted significance level of <0.0125 ($0.05 / 4$ comparisons) and a 98.75% confidence interval (CI). For each group, both estimated means and their corresponding standard error of estimates at each assessment point will be presented. In presenting between-group differences, mean differences with CIs will be presented. SPSS “MIXED” function will be used in analyzing our primary outcomes.

Secondary and tertiary outcome analyses

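### The Bonferroni-tested 24-week contrasts depend on a Group-by-Time test that has no stated alpha, is not needed for error control, and costs material power only if effects are smaller or less graded than planned

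*Protocol*

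**What the plan says.** The section on co-primary endpoint analyses, worded alike in the Protocol and the SAP, fits "an analysis of a 3 (Group) by 3 (Time) mixed-effects model with repeated measures" at baseline, 4 and 6 months. It then continues: "In the presence of a Group by Time interaction effect, follow-up pair-wise comparisons, using independent t tests, will be performed". The contrasts are enhanced versus standard tai ji quan and enhanced versus stretching, on change from baseline to 24 weeks, for MoCA and for dual-task cost. That makes two contrasts on each of two outcomes.

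The same section sets the level: "Our primary outcome analyses will be 2-sided with an adjusted significance level of <0.0125 (0.05 / 4 comparisons"), with 98.75% intervals. The interaction test is given no level of its own.

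The statistical analysis row of the Protocol synopsis repeats the condition. It then says that primary results will be given as the two between-group differences with a 98.75% interval, and does not tie that sentence to the interaction. Under descriptive analyses, 24-week change by group is to be shown for every outcome in any case.

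The power section does not mention the gate. It describes the effect size as "detectable with at least 80% power using a 2-sided 0.05-level test".

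**The concern.** The primary hypothesis is that enhanced training is better than each comparator at 6 months. The gate tests something else. A 3 by 3 interaction has (3 − 1) × (3 − 1) = 4 degrees of freedom, so it also draws on the 4-month visit and on standard tai ji quan versus stretching. Neither belongs to the primary hypothesis. The Protocol places the main cognitive integration phase of the enhanced arm in weeks 16 to 24, so the enhanced-versus-standard difference at 4 months may be small.

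Two things are at stake. First, the primary decision rule is incomplete: two analysts could use different levels for the gate, or treat a failed gate differently, and reach different primary conclusions from the same data. Second, a contrast that would be significant at 0.0125 can be blocked by a test that error control does not require.

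**Working it through.** **Inputs.** From the power section: 267 evaluable participants allocated 1:1:1, so 89 per arm; a difference versus standard "in mean MoCA change of 1.5 points (SD = 3.5") and a difference versus stretching "of 3 points (SD = 3.5"); correlation 0.7; 15% loss. From the co-primary section: two-sided 0.0125. Assumed, because the documents are silent: a gate alpha of 0.05 or 0.0125, and a 4-month effect that is a fraction f of the 6-month effect. SD 3.5 is taken as the SD of change.

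**Step 1. Reproduce the plan's figure.** The standardised difference is 1.5 / (3.5 × √(2/89)) = 2.859. At two-sided 0.05, power is Φ(2.859 − 1.960) = 81.6% (81.2% by noncentral t), which agrees with the stated figure of more than 80%. Also 267 / 0.85 = 314.1, so 315 enrolled. At 0.0125 with no gate, power is Φ(2.859 − 2.498) = 64.1% (63.2% by t) for 1.5 points and 99.9% for 3 points.

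**Step 2. Is the gate needed for error control?** No: 4 × 0.0125 = 0.05 bounds the family-wise error by itself. In simulation under the global null, per-contrast error is about 1.25% ungated, 0.8% with a 0.05 gate and 0.3% with a 0.0125 gate.

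**Step 3. How often does the gate open?** In a random-intercept model with complete data, the within-person variance is 3.5² / 2 = 6.125. The noncentrality of the interaction test is λ = 89 × D × T / 6.125, referred to F on 4 and 528 df. D is the sum of squared deviations of the three arm effects at 6 months. T is the same for the time profile (0, f, 1), that is (2/3)(1 − f + f²). T is 2/3 when f = 0 or 1, and lowest, at 1/2, when f = 1/2. Half the effect at 4 months is therefore the worst case for the gate between none and all.

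| 6-month advantage over standard / stretching | D | λ, f = 1/2 | Gate opens at 0.05 / 0.0125 | λ, f = 0 | Gate opens at 0.05 / 0.0125 |
|---|---|---|---|---|---|
| 1.5 / 3 (planned) | 4.5 | 32.7 | 99.9% / 99.3% | 43.6 | about 100% / about 100% |
| 1.5 / 1.5 | 1.5 | 10.9 | 75.3% / 56.1% | 14.5 | 87.7% / 73.5% |
| 1.0 / 1.5 | 1.167 | 8.5 | 62.9% / 41.8% | 11.3 | 77.1% / 58.3% |

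Gated power cannot exceed the chance that the gate opens.

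**Step 4. Power for the contrasts.** This comes from simulating the same model: the interaction F test, then t tests on 6-month change at 0.0125. There were 20,000 trials per scenario in the main run (Monte Carlo error at most 0.35 points), and repeat runs agreed to about a point. In the last three rows, ranges run from half the effect to no effect at 4 months. The first two rows use half the effect.

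| Scenario and test | No gate | Gate 0.05 | Gate 0.0125 |
|---|---|---|---|
| Planned 1.5 / 3: versus standard | 63.5% | 63.5% | 63.5% |
| Planned 1.5 / 3: versus stretching | 99.9% | 99.8% | 99.2% |
| 1.5 over both: one contrast | about 63% | 59–62% | 48–57% |
| 1.5 over both: at least one contrast | about 79% | 72–77% | 55–68% |
| 1.0 / 1.5: versus stretching | about 63% | 56–60% | 40–50% |

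**Step 5. Sensitivity to the SD.** If 3.5 is the SD of a single measurement, the SD of change is 3.5 × √(2 × 0.3) = 2.71. One contrast at 1.5 points over both then has 87.6%, 86.4% and 80.5% power (half the effect at 4 months).

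**The case against.** The strongest reply is that the plan expects graded effects: 1.5 and 3 MoCA points, and 10% and 20% for dual-task cost. With the MoCA effects the gate opens almost every time. That stands, and a reader who infers that the gate underpowers the trial as designed would be wrong.

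The larger losses need flatter or smaller effects, and the largest also need a gate at 0.0125. The text derives 0.0125 from four comparisons, and the interaction is not one of them. The phrase "Our primary outcome analyses will be 2-sided with an adjusted significance level of <0.0125" could be stretched to cover it, but that is not the natural reading. With a 0.05 gate and no 4-month effect, the loss on a single contrast at 1.5 points over both is only about 1 point. That also stands.

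Flatter effects are not far-fetched, however. The power section itself speaks of "a clinically meaningful improvement of at least 1 score unit in MoCA" and of a 10% reduction in dual-task cost against each comparison arm, without grading the two.

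A reader might also infer that a failed gate means the primary differences go unreported. The documents do not support that as fact. The synopsis promises the differences with intervals, and group changes and estimated means are to be shown regardless. What is missing is a statement of which sentence governs if the interaction is absent.

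Finally, the gate does not inflate error; it only makes testing more conservative. The larger loss of MoCA power, from 81.6% to 64.1%, comes from sizing at 0.05 and testing at 0.0125. It is there with or without the gate and is a separate matter.

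**Conclusion.** The point holds as a redundant and under-specified step in the primary decision rule, not as a flaw in validity. The gate is applied separately to each co-primary outcome, has no alpha and no stated consequence, and does not test the primary hypothesis.

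Its cost for MoCA is under 1 percentage point at the planned effects. If enhanced training is 1.5 points better than both comparators, the loss in power for at least one contrast is about 2 to 7 points with a 0.05 gate (79% to 77% or 72%) and 11 to 24 points with a 0.0125 gate (79% to 68% or 55%).

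These sizes rest on complete data, 89 per arm, an SD of change of 3.5, a random-intercept covariance structure and the assumed gate alpha and 4-month effect. No figure can be given for dual-task cost, because the documents state no SD for it.

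**What to change.** For the co-primary outcomes, delete the clause that makes the pairwise comparisons depend on the interaction. It appears in the Protocol synopsis and in the co-primary endpoint analyses of both the Protocol and the SAP. State that the four 24-week contrasts are always estimated, tested at 0.0125 and reported with 98.75% intervals, and that the interaction test is descriptive.

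This is a free improvement. Family-wise error stays at or below 0.05, power can only stay the same or rise, and neither sample size nor data collection changes. If the clause is kept, the minimum is to state the alpha of the interaction test and what is tested and reported when it is not met.

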
	1. change in Everyday Cognition (score range: 1 to 4)		
	2. change in Geriatric Depression Scale score (score range: 0 to		
	15)		
	3. change in Pittsburgh Sleep Quality Index global score (score		
	range: 0 to 21)		
	4. change in EuroQol EQ-D5 utility score (score range: -1 to 1)		
Covariates	There are no pre-specified covariates for the primary and secondary		
	endpoints.		
Follow-up schedule	16 weeks (mid point), 24 weeks (intervention termination), 48 weeks		
,	(post-intervention follow-up)		
Masking	Outcome assessors, data analysts		
Number of subjects	The target sample size is 315 participants to provide 80% power to		
3	detect a medium-size difference in mean MoCA change of 1.5 points		
	between the cognitively enhanced tai ji quan and the standard tai ji		
	quan groups and a large-size difference of 3 points between the		
	cognitively enhanced tai ji quan and the stretching control groups at 24		
	weeks.		
Statistical analysis	The effect of the intervention on the primary endpoints will be		
	evaluated using the intention-to-treat approach, in which participants		
	are grouped according to randomization assignment. To compare		
	change in outcome measures among the three intervention groups at 6		
	months, we will analyze a 3 (Group) by 3 (Time) mixed-effects model		
	with repeated measures on the second factor (i.e., outcome measures		
	assessed at baseline, 4 months, and 6 months). In the presence of a		
	Group by Time interaction effect, pre-specified follow-up pair-wise		
	comparisons will be performed to determine between-group		
	differences (indicated below). Secondary outcomes will be similarly		
	analyzed. Results from primary analyses will be presented as the		
	difference in mean MoCA and dual-task performance between the		
	cognitively enhanced tai ji quan and standard tai ji quan groups and		
	between the cognitively enhanced tai ji quan and the stretching		
	exercise control, with a Bonferroni-adjusted 2-tailed significance level		
	of .0125 for each of the two primary outcomes and a 98.75%		
Intonia analysis	confidence interval.		
Interim analysis	No interim analyses for efficacy or futility. However, interim		
	monitoring is performed with a focus on subject accrual, intervention		
	fidelity, protocol adherence, data completeness and quality, and		
	intervention safety and analysis.		

Study Background and Rationale

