To augment our paper-and-pencil measures, we will also employ Cogstate (cogstate.com), a set of customized, computerized tasks taxing verbal learning, including (a) International Shopping List Task plus a recall (the number of correct responses is used as the unit of measurement); (b) attention (Identification [speed of performance]); (c) working memory (One Back Task [speed of performance]); (d) visual recognition memory/attention (One Card Learning Task [accuracy of performance]); and (e) executive function (Groton Maze Learning Task [accuracy of performance]). These assessments are performed on a desktop computer and administered according to guidelines. The test session takes about 45 minutes to complete, with a practice before every task. Similar to the paper-and-pencil tests, a composite cognitive score will be calculated from these computerized cognitive tests.

Physical Performance

Functional Reach. In an upright standing position, this measure (measured in inches) assesses the maximal distance the participant can reach forward, beyond arm's length, while maintaining a fixed based of support in the standing position.²⁷

Short Physical Performance Battery (SPPB). This measure includes (1) increasingly challenging standing balance tasks (side-by-side stand, semi-tandem stance, tandem stance), (2) a 4-meter walk (gait velocity) at normal pace, and (3) repeated chair stands (leg strength).²⁸ A single SPPB measure is used, with the scale score ranging from 0 points (worst physical function) to 12 points (best physical function).

Timed Up&Go (TUG) test. The TUG measure²⁹ is recorded in seconds (the time taken by an individual to stand up from a standard armless chair, walk a distance of 3 meters, turn, walk back to the chair, and sit down).

Covariates

There are no pre-specified covariates in this study.

Tertiary measures

These measures include the (a) Everyday Cognition scale,³⁰ (b) Pittsburgh Sleep Quality Index,³¹ (c) Geriatric Depression Scale,¹⁷ and (d) EuroQol EQ-5D for health-related quality of life.³² These measures, described below, are included in a paper survey completed by participants.

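### Free precision left unused: the MoCA contrasts use change from baseline without baseline adjustment, which at the plan's own correlation of 0.7 (equal SDs assumed) would cut variance by 15% and CI width by 8%

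*Protocol*

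**What the plan says.** The Co-primary endpoint analyses section (same text in the Protocol and the SAP) specifies a "generalized linear mixed model with random intercepts and fixed treatment effects for the primary outcomes", laid out as 3 groups by 3 times, with baseline as one of the three outcome times. If the interaction is present, "follow-up pair-wise comparisons, using independent t tests, will be performed to identify a priori specified between-group differences". The quantity compared is "change in MoCA and costs of dual task in gait performance from baseline to 24 weeks", for enhanced versus standard tai ji quan and for enhanced tai ji quan versus stretching. Each test is two-sided at 0.0125 with a 98.75% CI.

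Baseline score has no covariate role anywhere. The Protocol's Covariates section says "There are no pre-specified covariates in this study", and the Synopsis says "There are no pre-specified covariates for the primary and secondary" endpoints. The Descriptive analyses section allows adjustment only for characteristics that differ significantly at baseline, and then only by "controlling for them as covariates in supplements to the main analyses".

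The power section for MoCA begins "Assuming two (pre and post) repeated measurements and a between-level correlation of 0.7", with an SD of 3.5, 267 evaluable participants, and differences of 1.5 and 3 points. For the other co-primary it says "Using the same assumptions, at 6 months, we estimated a 10% reduction in dual-task walking costs" and gives no SD.

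**The concern.** A change score fixes the weight on baseline at 1. The least-variance weight is the regression slope of follow-up on baseline, which is 0.7 when the correlation is 0.7 and the SDs are equal. The plan therefore carries avoidable noise. This is a loss of efficiency, not bias.

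The mixed model does not recover the loss. Its baseline means are free in each arm, so on complete data its 6-month Group by Time contrast is the same unadjusted difference in mean change. The plan also leaves open whether the t tests or the mixed model supply the reported CIs: the co-primary section names t tests and then SPSS MIXED, while the missing-data section pools a linear mixed model.

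At stake is mainly the enhanced versus standard contrast, which has the smaller target difference. Randomization follows the baseline assessment, so every randomized participant should already have the score.

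**Working it through.** **Inputs (power section and co-primary section).** 267 evaluable, so 89 per arm; correlation r = 0.7; SD 3.5; difference 1.5 points; power computed at two-sided 0.05; analysis at two-sided 0.0125. The documents give no separate baseline and follow-up SDs, so equal SDs is an assumption.

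**The plan's own figure.** Reading 3.5 as the SD of change, a two-sample t test at 0.05 has 81% power (0.811, noncentral t, 176 df), which agrees with the stated figure of more than 80%. Also 267/0.85 = 314.1, rounded up to 315.

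**Variance factors, as multiples of the raw variance s².**
- Change score: 2(1 − r) = 2 × 0.3 = 0.60
- Baseline-adjusted: 1 − r² = 1 − 0.49 = 0.51
- Variance ratio: 0.51/0.60 = 0.85, which equals (1 + r)/2
- CI width ratio: √0.85 = 0.922, so 7.8% narrower
- Effective size: 89/0.85 = 104.7, so 89 per arm act like about 105

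These ratios do not depend on what the SD of 3.5 refers to.

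**Does the planned mixed model already capture this?** With raw SD 3.5/√0.60 = 4.52, the generalized least squares variance of its 6-month contrast is 0.2753. The change-score t test gives 2 × 3.5²/89 = 0.2753, the same. Constraining the arms to a common baseline mean gives 0.2340, a ratio of 0.85.

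**Power and precision for 1.5 points, 89 per arm** (noncentral t; 176 df for change, 175 for adjusted).

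| Reading of SD 3.5 | SD, change → adjusted | Power at 0.0125 | Power at 0.05 | 98.75% half-width, points |
|---|---|---|---|---|
| SD of change | 3.50 → 3.23 | 63.2% → 71.8% | 81% → 87% | 1.32 → 1.22 |
| SD of raw score | 2.71 → 2.50 | 87.7% → 92.9% | 96% → 98% | 1.03 → 0.95 |

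For the 3-point contrast, power at 0.0125 is at least 99.9% with either method, so only the interval narrows.

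**Sensitivity** (SD of change held at 3.5, starting from 63.2% at 0.0125). With unequal SDs and k = follow-up SD/baseline SD, the ratio is k²(1 − r²)/(1 + k² − 2rk).

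| r | k | Variance ratio | CI narrower by | Adjusted power |
|---|---|---|---|---|
| 0.5 | 1 | 0.75 | 13% | 78% |
| 0.7 | 1 | 0.85 | 8% | 72% |
| 0.9 | 1 | 0.95 | 3% | 66% |
| 0.7 | 0.9 | 0.75 | 13% | 78% |
| 0.7 | 1.1 | 0.92 | 4% | 68% |
| 0.7 | 1.2 | 0.97 | 2% | 65% |

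**Simulation check.** Two separate runs of 20,000 simulated trials at r = 0.7, which include the cost of estimating the slope, gave variance ratios of 0.848 and 0.856. The first, with a true difference of 1.5, returned a mean estimate of 1.50 from both methods and power of 62.9% versus 71.4%.

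**The case against.** The strongest objection is timing. The title page cites a primary report of 31 October 2023, and both documents were last updated on 12 September 2024. A model added once results are known cannot restore confirmatory power at 0.0125. This stands, and it limits the remedy for results already reported.

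Second, the gain depends on more than the meaning of SD 3.5. It could be only 2 or 3 percentage points of power if r is near 0.9 or the follow-up SD is 1.2 times the baseline SD. This also stands, and the sensitivity table shows it. The direction is secure: in large samples the adjusted variance never exceeds the change-score variance, and the two tie only at k = 1/0.7 = 1.43.

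Third, the calculation uses complete cases, whereas the primary analysis uses multiple imputation, and Table 2 projects 90% completeness at 6 months. With 94 per arm (315 × 0.90/3 = 94.5, rounded down) power goes from 66% to 75%, a similar gain. No figure was computed under imputation.

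Fourth, change is the declared endpoint. Adjustment does not alter that: with baseline in the model, the arm coefficient is identical whether the response is the follow-up score or the change.

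Fifth, the low 63% comes mostly from powering at 0.05 and testing at 0.0125. That is true and a separate matter.

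**Conclusion.** The point holds as a worthwhile efficiency gain; the planned analysis is not in error. At r = 0.7 with equal SDs, the MoCA contrasts lose 15% in variance and 8% in CI width. For the 1.5-point contrast at 0.0125 that is 5 to 9 percentage points of power, depending on the reading of SD 3.5; other correlations or SD ratios move it as tabulated.

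For dual-task cost a gain is expected, but the documents give no SD and carry the correlation over only by reference. For secondary outcomes they give no correlation. No size is claimed for either. The 48-week CDR-SB analysis is outside this point because it has its own growth model.

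**What to change.** Take the four primary contrasts and their 98.75% CIs from one mixed model per outcome. Use the 4- and 6-month scores as responses, baseline score as covariate (or baseline kept as a response with arm means constrained equal), arm-by-visit means, and an unstructured within-person covariance. State that these are the reported estimates and that they still measure the between-arm difference in change. Drop the separate t tests.

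Fit the same model to the 10 imputed data sets, and name arm and baseline score among the imputation predictors; the current list names neither. Use the same form for the 48-week analyses other than CDR-SB.

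The cost is SAP wording, a few lines of SPSS MIXED and about one degree of freedom. No new data are needed. For results already reported, label it a sensitivity analysis; it can be pre-specified only for analyses not yet run.
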